### **Sample size justification.**

**Pilot patients:** N=21 pilot patients were enrolled prior to the start of the study to familiarize the study team with the protocol and identify any systematic issues that might result in protocol modifications. In the below sample size calculations we used data on these patients to help estimate the standard deviation of the primary outcome (pain score) and the within-subject correlation on the pain score across the 7 measurement times.

**Required Sample Size.** We plan the study to have 90% power at the 0.05 significance level to detect a difference in mean pain score of 1.25 or more between groups when measured over 10 minutes intervals during the first 60 minutes in the recovery period and analyzed using a linear mixed effects regression model. Based on our pilot study data (N=21) and previous work (SOLAR study report, Figure 1) we estimate the standard deviation of the pain score to be about 2.5 and the within-subject correlation to be approximately 0.60 when assumed to be exchangeable across measurements. Making these assumptions we would need a total of 116 patients before accounting for interim analyses, and a maximum of 144 after adjusting for planned interim analyses at each 1/4 of the maximum sample size. We therefore plan to randomize and enroll a maximum of 144 patients under these assumptions.

**Interim analyses.** We will conduct interim analyses for efficacy and futility at each 1/4 of the maximum sample size using a group sequential design and conservative gamma spending function parameters of -2 for efficacy and 0 (more aggressive) for futility. If the alternative hypothesis effect size (1.25 point difference) is true in the population sampled from, with the planned sample size we will cross an efficacy or futility boundary at each of the 4 looks with respective cumulative probabilities of 0.16, 0.50, 0.78 and 1.0.

Z-statistic boundaries for efficacy (futility) will be  $> 2.80$  ( $\leq 0.156$ ),  $> 2.58$  ( $\leq 0.667$ ),  $> 2.34$  ( $\leq 1.42$ ), and  $> 2.09$  ( $\leq 2.09$ ). The average total sample size across many simulations, assuming the alternative hypothesis is true (a true difference of 1), is N=64.

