**Simulations with Effect Size Larger Than Planned.** With the given design and corresponding stopping rules, if the true effect size (difference of 1.25 in mean pain score) is large than planned, the probability of crossing an efficacy boundary earlier in the trial will be proportionately increased. For example, if the true difference is 1.5, the cumulative probability of crossing a boundary (either efficacy or futility) in the 1st through 4th looks will be approximately 0.21, 0.62, 0.91 and 1.0, with average total sample size across many simulations was 81 patients.

**Internal Pilot Study to Reassess Standard Deviation and Within-Patient Correlation.** At the second interim analysis we will conduct an internal pilot study to reassess the standard deviation and within-patient correlation using the observed data for the primary outcome. Without considering the observed treatment effect, in a blinded fashion, we will use the observed within-patient correlation from the linear mixed effects model and the standard deviation at each time point to reassess the maximum required N to have 90% power at the 0.05 significance level to detect a difference of 1.25 or more in pain score. If the required sample size is at least 10% higher than initially planned, the Executive Committee will decide whether to recommend that the maximum sample size be

increased to maintain 90% power. There is no statistical penalty for this internal pilot re-estimation of the within-patient correlation “nuisance parameter”.

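### The stated average sample size of 64 contradicts the section's own stopping probabilities (about 92) and its printed boundaries (about 84 to 87), and is tied to the wrong effect size

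*Combined protocol and SAP*

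**What the plan says.** All of the text is in the sample size justification.

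- **Required Sample Size** sets the target: "We plan the study to have 90% power at the 0.05 significance level to detect a difference in mean pain score of 1.25 or more". The inputs are SD 2.5, within-patient correlation 0.60, a total of 116 patients without interim looks and a maximum of 144 with looks at each quarter of the maximum.
- **Interim analyses**, stopping probabilities: "If the alternative hypothesis effect size (1.25 point difference) is true", then "we will cross an efficacy or futility boundary at each of the 4 looks with respective cumulative probabilities of 0.16, 0.50, 0.78 and 1.0".
- **Interim analyses**, boundaries: efficacy is declared above 2.80, 2.58, 2.34 and 2.09, and futility at or below 0.156, 0.667, 1.42 and 2.09. The spending parameters are gamma -2 for efficacy and 0 for futility.
- **Interim analyses**, average size: "The average total sample size across many simulations, assuming the alternative hypothesis is true (a true difference of 1), is N=64".
- The paragraph headed **Simulations with Effect Size Larger Than Planned** gives, for a true difference of 1.5, cumulative probabilities of 0.21, 0.62, 0.91 and 1.0 for crossing either boundary, "with average total sample size across many simulations was 81 patients".

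**The concern.** The section gives the alternative hypothesis two values, 1.25 and 1. It also gives an average size that cannot be obtained from the stopping probabilities printed just before it. The order is wrong too: a larger true effect should end the trial sooner, as the plan itself says, yet the average is 64 under the alternative and 81 at 1.5 points.

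These figures tell a reader, the IRB and whoever oversees the interim looks how long the trial is likely to run and how likely it is to stop at each look. If they conflict, that expectation is unreliable. The check also shows that one decision threshold, the futility rule, can be read in two ways.

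**Working it through.** **1. Average size from the stated probabilities.** Average N = sum over looks of P(stop at look k) × N_k, with N_k = 36, 72, 108, 144.

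- 1.5 points: 36(0.21) + 72(0.41) + 108(0.29) + 144(0.09) = 81.4. The plan says 81, so it is reproduced and the formula is evidently the plan's own.
- 1.25 points: 36(0.16) + 72(0.34) + 108(0.28) + 144(0.22) = 92.2. The plan says 64. Allowing for rounding of the probabilities, the range is 91.6 to 92.7.

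**2. Average size from the printed boundaries.** The Z statistics at information fractions 0.25, 0.5, 0.75 and 1 were evaluated by numerical integration and by simulation. Two values of the drift (the expected final Z at 1.25 points) were used:

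- 3.70 from the stated inputs. The SD of a patient's mean over 7 scores is 2.5 × √((1 + 6 × 0.6)/7) = 2.027, and 1.25 / (2.027 × √(4/144)) = 3.70.
- 3.594, which gives exactly 90% power with the printed bounds applied to |Z|.

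The futility bound was applied to Z as printed, and also to |Z|.

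| True difference | Z, drift 3.594 / 3.70 | \|Z\|, drift 3.594 / 3.70 | Plan |
|---|---|---|---|
| 0 | 60.8 | 87.4 | not given |
| 1.0 | 93.4 / 92.7 | 96.9 / 96.0 | 64 by its label |
| 1.25 | 85.1 / 83.5 | 86.8 / 85.0 | 64 by its definition |
| 1.5 | 74.0 / 72.0 | 74.7 / 72.6 | 81 |

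The average peaks at a difference of about 0.75 to 0.85 and falls after that, so at 1 or 1.25 points it must exceed the value at 1.5. An average of 64 needs a true difference of about 1.69 to 1.75.

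**3. Cumulative crossing probabilities.**

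| | Look 1 | Look 2 | Look 3 | Look 4 |
|---|---|---|---|---|
| 1.25, plan, labelled either boundary | 0.16 | 0.50 | 0.78 | 1.0 |
| 1.25, efficacy only, drift 3.594 | 0.158 | 0.498 | 0.776–0.782 | 0.888–0.900 |
| 1.25, either boundary | 0.18–0.22 | 0.55–0.59 | 0.86–0.88 | 1.0 |
| 1.5, plan, labelled either boundary | 0.21 | 0.62 | 0.91 | 1.0 |
| 1.5, either boundary | 0.27–0.30 | 0.71–0.75 | 0.94–0.96 | 1.0 |

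The first three stated values at 1.25 points are efficacy-only probabilities. The final 1.0 is right only for either boundary. This mixture explains why the stated row averages 92 and the boundaries about 85. The 1.5-point row agrees with its own average but not with the boundaries.

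**4. Z or |Z| for futility.** With gamma 0 and 90% power, a quarter of the type II error, 0.10/4 = 0.025, is spent at look 1, where the expected Z is 3.594 × √0.25 = 1.797.

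- On |Z|: Φ(0.156 − 1.797) − Φ(−0.156 − 1.797) = 0.0504 − 0.0254 = 0.025, so 0.156 is reproduced.
- On signed Z: the bound would be 1.797 − 1.960 = −0.16, not 0.156.

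The printed thresholds therefore come from a |Z| design but are written as signed limits. With no true difference, the chance of stopping at look 1 is 0.565 as printed and 0.129 on |Z|.

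**The case against.** The strongest reply is that this is a unit slip. 92.16/144 is exactly 0.64, so 64 may be a percentage of the maximum printed as a patient count. The stated probabilities and the average would then agree, and 92 would sit correctly above 81. The 1-point label could be left over from the primary hypothesis, which names 1 point as clinically meaningful. This is plausible, but the documents do not say it, and the printed count and label remain wrong.

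The replacement value also depends on choices. Seven scores give a fixed total of 112 rather than the stated 116, so the 3.70 drift is slightly generous. A simulation with t statistics and signed bounds gave 82 to 83. If futility crossings were not enforced, the average at 1.25 points would be 91.8 (drift 3.594) or 89.4 (drift 3.70). That departs from the plan, which stops for futility, and it still does not give 64. The final figure should therefore come from a rerun by the trial statisticians.

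Finally, average size enters no stopping rule or enrolment limit; the maximum of 144 governs. On |Z| with drift 3.594, the either-boundary gaps are small at the early looks (0.16 against 0.18, 0.50 against 0.55) and larger at look 3 (0.78 against 0.86). That limits the consequence, and the Z or |Z| question is a separate defect. Both points are fair. Neither makes the stated figures correct.

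**Conclusion.** The concern holds. The average of 64 matches neither the section's stated probabilities (92.2) nor its boundaries (83.5 to 86.8 at 1.25 points, 92.7 to 96.9 at 1 point). Against the boundaries at the planned effect it is too low by about 20 to 23 patients, or 23 to 26%; against the stated probabilities it is too low by 28. The 1-point label contradicts the 1.25-point alternative. The chance of having stopped by look 3 at 1.25 points is 0.86 to 0.88, not 0.78.

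The comparison with 92.2 uses only the plan's own numbers. The boundary-based figures assume equal quarters of 144, enforced futility stopping and a drift between 3.594 and 3.70. Power at 1.25 points stays near 90%, and neither the maximum nor the efficacy bounds are in question. It should be fixed, but it does not threaten the design.

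**What to change.** 1. State whether the futility thresholds apply to Z or |Z|, before any rerun. This settles a decision rule and is not mere rewording: with no true difference the average size is about 61 on signed Z and 87 on |Z|.
2. Rerun the design under its stated assumptions and restate the average size at 1.25 points. About 84 to 87 is expected if futility stops are enforced.
3. Change the parenthetical difference of 1 to 1.25.
4. Either relabel 0.16/0.50/0.78 as efficacy-only and give its own final value (about 0.89 to 0.90), or replace the row with either-boundary probabilities.
5. Restate the 1.5-point probabilities and average from the same run.

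The cost is one design run and a few sentences. The maximum of 144, the efficacy bounds and the power at 1.25 points do not change. The stated expected size becomes less favourable by about 20 to 23 patients.

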## Human Subjects Protection

The experimental device PMD-200 from Medasense, Ramat-Gan) is CE marked and has been sold and used in the European Union for 3 years, and in Canada for 2 years. However, the NOL device has yet to be submitted for FDA clearance. The proposed pilot trial is designed to provide information that will help the investigators, Medasense, and the FDA optimally design a Phase 3 multi-center trial that might support FDA approval.

Typical pain scores during the initial phase of post-anesthetic recovery at the Cleveland Clinic Main Campus are 7/10, indicating poor pain control. The only aspect of our protocol that is non-standard is opioid titration to NOL. Pain scores could hardly be worse with NOL guidance, and in all cases, clinical judgement will prevail. Standard vital signs monitoring will continue to be used per current routine care. Our experienced anesthesia attending will never give patients clearly inadequate or excessive doses.

An important consideration is that opioid under-dosing and over-dosing is easily correctable. Most patients at the Cleveland Clinic and world-wide are under-dosed (as indicated by typically high initial pain scores) which is ameliorated simply by giving additional opioid. Over-dosing is also not especially serious since opioids can be antagonized by administration of small repeated doses naloxone until the right residual opioid effect remains. We thus request a non-significant risk device exemption for the proposed pilot trial.

Supplemental material includes sedation and delirium instruments, CE certificates, and safety and design documentation.

The following Adverse Events (AE) will be collected:

- All AEs with an anesthesia-related cause
- All adverse device effects (ADE)
- All Serious Adverse Events (SAE) (including sepsis events or related to opioid therapy)

Pre-planned interventions or occurrence of endpoints, including deviations in vital signs, specified in the CIP are not considered AEs, if not defined otherwise

Definitions according to ISO 14155:2011 will be used in this study.

Where the definition indicates “device”, it refers to the [PMD-100](#).

**Table 1. Definition of Adverse Events and Device Deficiency**

| Term                          | Abbreviation | ISO Definition  |
|-------------------------------|--------------|---|
| Adverse Event                 | AE           | 
Any untoward medical occurrence, unintended disease or injury, or untoward clinical signs (including abnormal laboratory findings) in subjects, users or other persons, whether or not related to the investigational medical device.
 
NOTE 1: This definition includes events related to the investigational medical device or the comparator.
 
NOTE 2: This definition includes events related to the procedures involved.
 
NOTE 3: For users or other persons, this definition is restricted to events related to investigational medical devices.
 |
| Adverse Device Effect         | ADE          | 
Adverse event related to the use of an investigational medical device.
 
NOTE 1: This definition includes adverse events resulting from insufficient or inadequate instructions for use, installation, operation, or any malfunction of the investigational medical device.
 
NOTE 2: This definition includes any event resulting from use error or from intentional misuse of the investigational medical device.
  |
| Serious Adverse Device Effect | SADE         | Adverse device effect that has resulted in any of the consequences characteristic of a Serious Adverse Event.   |
| Serious Adverse Event         | SAE          | 
An adverse event that
 
a) led to death,
 
b) led to serious deterioration in the health of the subject, that either resulted in:
 

• a life-threatening illness or injury,

• a permanent impairment of a body structure or a body function,

• in-patient or prolonged hospitalization,

• medical or surgical intervention to prevent life-threatening illness or injury or

  |

| Term  | Abbreviation | ISO Definition  |
|---|--------------|---|
|   |              | 
permanent impairment to a body structure or a body function,
 
 
• led to fetal distress, fetal death or a congenital abnormality or birth defect.
 
 
NOTE: Planned hospitalization for a pre-existing condition, or a procedure required by the CIP, without serious deterioration in health, is not considered a serious adverse event.
 |
| Unanticipated Serious Adverse Device Effect | USADE        | 
Serious adverse device effect which by its nature, incidence, severity or outcome has not been identified in the current version of the risk analysis report.
  |
| Device Deficiency                           | DD           | 
Inadequacy of a medical device with respect to its identity, quality, durability, reliability, safety or performance.
 
NOTE: Device deficiencies include malfunctions, use errors, and inadequate labelling.
  |

## Reporting procedures

AE information will be collected throughout the study and reported to Medasense on an AE eCRF, one for each adverse event. It is the responsibility of the investigator to identify the occurrence of adverse events to ensure that the information is accurately documented in the medical record and on the eCRFs.

DD information will also be collected throughout the study and reported to Medasense on a Device Deficiency eCRF. DDs require immediate reporting if they did not lead to an adverse event but could have led to a serious adverse device effect (SADE):

- if either suitable action had not been taken,
- if intervention had not been made, or
- if circumstances had been less fortunate

AE documentation will include the following information at a minimum:

- Date of event
- Time of the event
- Diagnosis and description
- Actions taken / treatment (including vital signs, and date and time of rescue related actions when applicable)
- Assessment of seriousness
- Relatedness to the device
- Outcome or resolution and date of the resolution

For AEs that require immediate reporting, initial reporting may be done by phone, fax, e-mail, or preferably on the eCRF completing as much information as is available. The completed AE eCRF must be sent to Medasense as soon as possible.

In case the investigator requires information from the sponsor in an emergency situation, the investigator can contact Medasense team directly.

The sponsor will ensure timely Adverse Event reporting to meet global regulatory requirements.

**Table 2. Reporting Requirements for Events**

| Serious Adverse Device Effects (SADE), including Unanticipated Serious Adverse Device Effect (USADE): |  |
|--|--|
| Investigator submit to:   |  |
| Medasense  | Immediately after the investigator first learns of the event or of new information in relation with an already reported event. |
| Regulatory Authority   | As per local reporting requirement.  |
| EC/IRB   | Submit to EC/IRB per local reporting requirement.  |
| Sponsor submit to:  |  |
| Regulatory Authorities   | Reporting timeframe as per local requirement.  |
| EC/IRB   | Submit to EC/IRB per local reporting requirement.  |
| Serious Adverse Events (SAE)  |  |
| Investigator submit to:   |  |
| Medasense  | Immediately after the investigator first learns of the event or of new information in relation with an already reported event. |
| Regulatory Authority   | As per local reporting requirement.  |
| EC/IRB   | Submit to EC/IRB per local reporting requirement.  |
| Sponsor submit to:  |  |
| Regulatory Authorities   | Reporting timeframe as per local requirement.  |

|  |  |
|--|--|
| EC/IRB                                       | Submit to EC/IRB per local reporting requirement.  |
| Adverse Device Effects (ADE)          |  |
| Investigator submit to:               |  |
| Medasense                                    | Immediately after the investigator first learns of the event.  |
| Regulatory Authority                         | As per local reporting requirement.  |
| EC/IRB                                       | Submit to EC/IRB per local reporting requirement.  |
| Sponsor submit to:                    |  |
| Regulatory Authorities                       | Reporting timeframe as per local requirement   |
| EC/IRB                                       | Submit to EC/IRB per local reporting requirement.  |
| All other AEs                         |  |
| Investigator submit to:               |  |
| Medasense                                    | Submit in a timely manner after the investigator first learns of the event.  |
| Regulatory Authority                         | As per local reporting requirement.  |
| EC/IRB                                       | Submit to EC/IRB per local reporting requirement.  |
| Device Deficiency with SADE potential |  |
| Investigator submit to:               |  |
| Medasense                                    | Immediately after the investigator first learns of the deficiency or of new information in relation with an already reported deficiency. |
| Regulatory Authorities                       | As per local reporting requirement.  |
| EC/IRB                                       | As per local reporting requirement.  |
| Sponsor submit to:                    |  |
| Regulatory Authorities                       | As per local reporting requirement.  |
| EC/IRB                                       | As per local reporting requirement.  |
| All other Device Deficiencies         |  |
| Investigator submit to                |  |
| Medasense                                    | Submit in a timely manner after the investigator first learns of the deficiency.   |
| Regulatory Authorities                       | As per local reporting requirement.  |
| EC/IRB                                       | As per local reporting requirement.  |

## **Supplemental Material**

- 1) Richmond Alertness and Agitation Scale.
- 2) 3D Confusion Assessment Method for delirium.
- 3) Australian Register of Therapeutic Goods Certificate
- 4) EC Certificate
- 5) Medical Device License Canada
- 6) ISO Certificate
- 7) User Manual
- 8) Declaration Latex free raw material
- 9) Phthalate free declaration
- 10) RoHS Declaration 2019
- 11) Risk Management Plan
- 12) Evaluation of the NOL Index- Clinical Validation Studies
- 13) Clinical Evaluation Report
- 14) Summative Usability Validation Report

## **Funding**

This study project is an investigator-initiated project and is financially supported by Medasense Biometric Ltd., Ramat Gan, Israel.

- Protocol: we now specify for the NOL-guided opioid administration group, that NOL values above 25 **exceed 60 or more seconds**, before a fentanyl bolus should be given.
- Protocol: we now specify, that all patients will receive a morphine **PCA**, which will be activated upon arrival to **PACU**, per routine care.
- Measurements: we now define inadequate analgesia: **inadequate analgesia will be defined by systolic pressure  $\geq 140$  mmHg, heart rate exceeding 90 beats/min, MAP<65 mmHg. Vasoactive drugs and episodes and duration of hypotension (mean arterial pressure <65 mmHg, occurrences of MAP <60 & MAP <55) will be recorded. Muscle-relaxant administration will be recorded as well.**
- Measurements: we now define documented medications and measurements in more details: **The following will be recorded on the PMD-200 monitor, using the EVENTS button, as accurately as possible: Medications administration: Fentanyl, Vasoactive drugs, Muscle relaxants, Reversal agents; Events: Induction, Intubation, Foley catheter placement, Incision, Insufflation, Trocar insertion, Discontinuation of sevoflurane, Extubation.**
- We added two paragraphs about **Adverse Events** and **Reporting procedures**.

- Title: “benefits” was replaced by “consequences”
- Several Co-investigators have been added.
- Aims and hypothesis have been revised.
- Methods: subject selection. “We will enroll up to 144 adult patients.” (replaced 30 cases)
- Inclusion criteria: “Morphine PCA as clinical standard postoperatively” was removed and is now considered optional
- Number of pilot patients: we will now enroll up to **25 pilot patients** (replacing 10 patients)
- Study protocol: Routine opioid management. We now specify the bolus of fentanyl: **“Boluses of fentanyl 1 µg/kg actual body weight (ABW), up to a maximum dose of 100 µg per bolus”** ...Towards the end of the surgery (approximately 30-45 minutes before end of surgery, based on clinical judgment), the boluses of fentanyl will be reduced to 0.5 µg/kg ABW, up to a maximum of 50 µg per boluses. Boluses will be given per clinical judgment.
- Study protocol: NOL guided opioid administration. We now specify the bolus of fentanyl.”NOL values exceeding 25 for more than 30 seconds will typically be treated with boluses of fentanyl 1µg/kg ABW, up to a maximum of 100 µg per boluses, 5-minute intervals. Towards the end of the surgery (approximately 30-45 minutes before end of surgery, based on clinical judgment), the boluses of fentanyl will be reduced to 0.5 µg/kg ABW, up to a maximum of 50 µg per boluses, 5 minutes intervals. The target of a NOL score below 25 will be maintained until surgery ends.”
- Study protocol: NOL-guided opioid administration. Time above a NOL threshold above 25 exceeding **30 seconds** (replaced 60 seconds).
- Study protocol: NOL-guided opioid administration. **“Boluses of fentanyl 1 µg/kg actual body weight (ABW), up to a maximum dose of 100 µg per bolus”**
- Study protocol: we now standardize the preemptive bolus of opioid at the end of surgery: **Approximately 20-30 minutes before end of the surgery, a preemptive bolus of hydromorphone will be given intravenously per clinical routine;**
  - Patients younger than 70 years: 0.4 mg of hydromorphone for patients with an ABW <60 kg and 0.6 mg of hydromorphone for patients with an ABW > 60 kg
  - Patients aged between 70 and 75 years: 0.4 mg of hydromorphone,
  - Patients older than 75 years: 0.2 mg of hydromorphone.
- The section on statistical analysis has been entirely revised.
